7.4. Study Medication Weights

A study staff member will weigh the study medication bottles with the cap prior to dispensing to the subject and after collection of the study medication bottles during study treatment visits. The weights should be recorded in the source documents. Bottles that are not dispensed to the subject do not need to be weighed.

7.5. Treatment Compliance

The investigator or designee will be responsible for monitoring subject compliance through questioning the subject, documenting missed doses, if any, weighing the bottle before dispensing and after return and visual inspection of the quantity in the study medication bottles (used and unused). Study staff will counsel the subjects, as required to make sure subjects are compliant with study medication applications. The subject will be given a calendar to complete to confirm administration of twice-daily doses.

7.6. Dose Modification

If the subject experiences application site AE(s), study medication may be stopped for up to a total of 3 days or the frequency of study medication application may be reduced from twice-daily to once-daily for up to a total of 6 days. Dose interruptions must be documented in the source document and eCRF. Dose modifications greater than these must be reviewed and approved by the Medical Monitor. Refer to Section 9.2.4 for Study Medication Interruption or Discontinuation due to related SAEs or specific abnormal laboratory values.

7.7. Study Medication Accountability

The Principal Investigator or designee is responsible for ensuring accountability for the investigational agent, including reconciliation of medications and maintenance of medication records. Upon receipt of study medication, the clinical site will check for accurate delivery and acknowledge receipt by signing (or initialing) and dating the shipment documentation provided. One copy of this document will be returned to Aclaris Therapeutics, Inc. (or designee) and one copy will be maintained in the study file. In addition, an accurate study medication disposition record will be kept, specifying the amount dispensed for each subject and the date of dispensing. This inventory record will be available for inspection at any time. At the completion of the study, the original inventory record will be available for review by Aclaris Therapeutics, Inc. upon request. Final medication accountability will be performed by the study monitor at the completion of the study and all used and unused study medication bottles will be returned to Aclaris Therapeutics, Inc. or designee for disposal.

7.8. Other Study Supplies

Aclaris Therapeutics, Inc. or a third party will provide:

- Supplies and instructions for collecting, labeling, shipping and result reporting for the clinical laboratory tests and urine pregnancy tests
- A scale to weigh the study medication bottles.
- Equipment, supplies, and training for taking standardized photographs
- Equipment, supplies, and training for performing standardized ECGs
- Study medication applicators
- An insulated lunch box to transport study medication

7.9. Blinding

The study is an open-label study.

7.10. Study Medication Packaging, Labeling, Storage and Security

The study medication must be used by the study subjects only. Investigational site staff will explain the application of the study medication to subjects.

Study medication will be provided by Aclaris Therapeutics, Inc. and labeled according to regulations. Study medications must be stored in a secure area with limited access under appropriately controlled and monitored storage conditions. Study medication should be stored at controlled room temperature 59°F - 77°F (15°C – 25°C). Subjects will be instructed to store the study medication in the original glass bottle (in the carton provided) at room temperature, away from heat, moisture, direct light, and to keep it from freezing and out of the reach of children.

The study medication will be supplied in amber glass 30-mL bottles with a 20-mL fill. Disposable applicators will be provided.

One Subject Kit box will contain 24 bottles, in individual boxes and disposable applicators. Each kit will be labeled with a single-panel label. Each box and bottle will be labeled with a single panel label.

Additional supplies will be packaged in amber glass 120 ml (100 mL fill) bottles in individual cartons. Each carton and bottle will be numbered with a unique number and labeled with a single-panel label.

8. STUDY ASSESSMENTS

The investigator, a designated and appropriately trained staff member (*e.g.*, subinvestigator) or the subject will perform the study assessments according to the schedules noted below.

The same individual should perform the assessments for a given subject throughout the study. If this becomes impossible, an appropriate designee with overlapping experience with the subject and the study should perform the assessments.

Similar lighting conditions and subject positioning should be used for all evaluations for a given subject. A Wood's lamp should be used to assess the subject's vitiliginous lesions.

8.1. Assessments of Efficacy

8.1.1. Canfield 2D Digital Facial Image Analysis

A qualified investigational staff member will take 18 photographs (5 lighting modalities x 3 views [left, front, right]) of the face at baseline and then monthly during the study. Each imaging session includes a sequence of images including the following lighting/capture modalities:

- Standard 1 (default settings) – General purpose white light photograph, the typical “clinical” photo. Provides balanced cross lighting for good subjective evaluation of most skin features.
- Standard 2 (default settings) – ‘Diffuse light’. Provides even, white light across the entire image with a minimum of highlight and shadow. Ideal for many quantitative image analysis applications.
- Cross Polarized (default settings) – Polarized light sources with a Perpendicular polarizer over the camera lens. Filters out surface reflections for superior visualization of sub-surface detail (vascular features, erythema, pigment, etc.)

- UV Fluorescence - NF (default settings) – UV filters (365nm band pass) over powerful strobes captured through an un-attenuated lens. The Fluorescence photo is geared toward enhancing the visibility of pigment features that absorb UV light. Fluorescing Porphyrin details are also visible.
- Parallel Polarized (default settings) – Polarized light sources with a Parallel polarizer over the camera lens. Passes only surface reflections for superior visualization of topographical data (wrinkles, fine lines, pores, etc.)

Equipment, supplies, training and detailed instructions for obtaining and managing photographs will be provided to the investigational center prior to the initiation of subject enrollment.

Canfield Scientific will conduct image analysis. The obtained cross-polarized image will be transformed using Canfield's RBX technique to separate melanin (Brown image) from hemoglobin (Red image). A segmentation algorithm detects hyperpigmentation (pigmented areas with concentration higher than normal skin concentration) and depigmentation (pigmented areas with concentration lower than normal skin concentration) within the areas of interest (AOI) from the RBX Brown images. Area of detected pigmentation and intensity measurements can be reported by the algorithm after segmentation. The measurement will be the ratio of the detected area of pigmentation and the AOI. The primary endpoint will be based on the quantification of depigmentation in the AOI over time.

Area of Interest

The AOI includes approximately 90% of the total facial surface area and is defined as the area from the border of the hairline to the jawline. Hair bearing areas such as the eyebrows and the areas of the forehead and chin covered by the stereotactic positioning device for photographs are not included in the AOI. Refer to APPENDIX 6 for a diagram of the AOI.

8.1.2. Facial Vitiligo Area Scoring Index (F-VASI) and Facial Total Body Surface Area (TBSA)

The F-VASI is an assessment of the subject's facial vitiligo modified from the VASI for the face only. The investigator or designee will assess the face using a Wood's lamp to assist in the identification of the vitiliginous lesions and then calculate the F-VASI score based on the descriptor that best matches the presentation of the subject at each individual visit: Baseline (Visit 2) and Visits 5, 6, 7, 8, 9, 10,11 (if applicable) and if continuing for 24 additional weeks of treatment, Visit 12-15. The investigator should not refer to any other visits assessments when performing the F-VASI.

The percentage of vitiligo involvement for the face is calculated using the palmar method. The palmar method uses the palmar surface area of the investigator's hand as an estimation guide and defines the surface of the hand including fingers to be 1.0% of the total body surface area.

At screening and baseline, the **Facial TBSA** will be calculated and must be at least 0.25% (excluding: the area from the eyebrows to and including the upper eyelids; the area from the bony rim of the orbit to and including the lower eyelids; mucosal lip areas, and the area of the chin and forehead covered by stereotactic photographic device) and include at least one area of normal pigmentation. The face is then clinically evaluated by visual assessment for the pattern

of skin depigmentation using a visual scale. The publication by Hamzavi I, Jain H, McLean D, Shapiro J, Zeng H, and Lui H. 2004 will be provided to the investigators to depict the pattern of depigmentation as illustrated in descriptive patient photographs.

Facial VASI = % BSA x residual depigmentation

- **BSA** - used as a guide to estimate % of vitiligo involvement of the face
- **Extent of residual depigmentation** is expressed by the following percentages:
 - 0
 - 10% - only specks of depigmentation are present
 - 25% - the pigmented area exceeds the depigmented area
 - 50% - the depigmented and pigmented areas are equal
 - 75% - the depigmented area exceeds the pigmented area
 - 90% - specks of pigment are present
 - 100% - no pigment is present

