5.3. Inclusion Criteria

In order to be eligible for the study, a subject must fulfill all of the following criteria:

1. Subject is a male or female \geq 18 years of age.
2. Subject has a clinical diagnosis of new onset or actively progressing non-segmental facial vitiligo or worsening of existing facial lesions within the past 6 months. Actively progressing vitiligo is defined as: subject history of a new vitiliginous lesion or objective signs of disease activity (such as: confetti-like depigmentation, trichrome lesions, and the Koebner phenomenon) as assessed by the investigator. Subjects may have non-facial vitiliginous lesions that are unchanged for more than 6 months provided they meet the requirement for active facial lesions.
3. Subject has non-segmental facial vitiligo effecting at least 0.25% total body surface area (TBSA) (excluding: the area from the eyebrows to and including the upper eyelids, the area from the bony rim of the orbit to and including the lower eyelids; mucosal lip areas; beard [if applicable]; and forehead and chin areas covered by the stereotactic positioning device for photography) with at least one area of the face with normal pigmentation. The face is defined as the area from the border of the hairline, not including hair bearing skin (eyebrows and beard, if applicable) to the jawline.
4. Women of childbearing potential (WOCBP) must have a negative serum pregnancy test at the screening visit and a negative urine pregnancy test at the baseline visit and must agree to use an approved method of highly effective birth control for the duration of the study and for 30 days after last study medication application.
5. If female, subject who is non-pregnant and non-lactating and not planning a pregnancy during the duration of the study.
6. Subject is in good general health and free of any known disease state or physical condition which, in the opinion of the investigator, would interfere with the study assessments or put the subject at undue risk by study participation.
7. Subject is willing and able to follow all study instructions and to attend all study visits.
8. Subject agrees to refrain from any other treatments for vitiligo from the screening visit through the final follow-up visit. Over the counter (OTC) preparations deemed acceptable by the investigator and camouflage makeups are permitted.
9. Subject is able to comprehend and willing to sign an Informed Consent Form (ICF).

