8.1.4. Vitiligo Area Scoring Index (VASI)

The VASI will be assessed by the investigator or designee to track the total body vitiligo status throughout the study at screening (Visit 1), baseline (Visit 2), Week 12 (Visit 7), Week 24 (Visit 10), and Week 48 (Visit 14). The body is divided into the following 6 separate and mutually exclusive sites: head/neck, hands, upper extremities (excluding hands), trunk, lower extremities (excluding feet), and feet. The investigator or designee will assess each of the 6 body sites using a Wood's lamp to assist in the identification of the vitiliginous lesions.

The percentage of vitiligo involvement for each body region is calculated using the palmar method. The palmar method uses the palmar surface area of the investigator or designee's hand as an estimation guide and defines the surface of the evaluator's hand including fingers to be 1.0% of the total body surface area. Each of the 6 body sites is then clinically evaluated by visual assessment for the pattern of skin depigmentation using a visual scale. The publication by Hamzavi I, Jain H, McLean D, Shapiro J, Zeng H, and Lui H. 2004 will be provided to the investigators to depict the pattern of depigmentation as illustrated in descriptive patient photographs.

Total body VASI = Sum of all the values from the body sites (in Hand units) x (Residual depigmentation)

- **Hand unit** - One hand unit is approximately 1% BSA – used as a guide to estimate % of vitiligo involvement in each body area. (Body is divided into 6 areas)
- **Extent of residual depigmentation** is expressed by the following percentages:
 - 0
 - 10% - only specks of depigmentation are present
 - 25% - the pigmented area exceeds the depigmented area
 - 50% - the depigmented and pigmented areas are equal
 - 75% - the depigmented area exceeds the pigmented area
 - 90% - specks of pigment are present
 - 100% - no pigment is present

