11.2. Statistical Methods

Summary descriptive statistics (N, mean, median, SD) by visit will be provided for all safety and efficacy parameters. Primary and secondary efficacy parameters are described below:

Primary Efficacy Parameter

Mean change from baseline in facial depigmentation in the AOI will be quantified using Canfield-2-D photographic image analysis from baseline (Visit 2) compared to Week 48 (Visit 14).

Secondary Efficacy Parameters:

Mean change from baseline in facial depigmentation will be calculated as the mean change in Facial assessment of the Vitiligo Area Scoring Index (F-VASI) from Visit 2 compared to Week 24 (Visit 10) and if applicable, Week 48 (Visit 14). F-VASI is a modification of the validated quantitative assessment scale for vitiligo which evaluates the percentage of vitiligo involvement of the face only.

Mean change from baseline in facial depigmentation in the AOI based on Canfield 2-D Photographic analysis from Visit 2 compared to Weeks 4, 8, 12, 16, 20, 24, 32, 40, and post-treatment Week 52 (Visits 5-11, and 12, 13, and 15).

Mean change from baseline in the Facial assessment of the Vitiligo Area Scoring Index (F-VASI) from Visit 2 compared to Weeks 4, 8, 12, 16, 20, 24, 32, 40, 48 and post-treatment Week 52 (Visits 5-11, and Visits 12, 13, 14 and 15).

Mean change from baseline in the VitiQoL from Visit 2 compared to Week 12, 16, 20, 24, and 48 (Visits 7-10, 14).

Treatment success based on the subject's assessment of vitiligo on the Vitiligo Noticeability Scale (VNS) at Week 4, 8, 12, 16, 20, 24, 32, 40, and 48.

Mean change from baseline in total VASI from Visit 2 to Visits 7 and Visit 14 (Week 48) will be assessed for descriptive purposes only to track disease progression in untreated areas.

Safety analyses will include descriptive statistics calculated on the safety parameters using the safety population. The proportion of subjects with treatment-emergent adverse events will be tabulated and presented by Medical Dictionary for Regulatory Activities (MedDRA) System Organ Class. Vital signs and clinically relevant abnormal laboratory results will also be tabulated and presented. Change from baseline in the Local Tolerability Assessments (LTA) to end of treatment (Visit 10) will be summarized.

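### Facial %BSA, F-VASI and total VASI are scaled to the assessor's hand rather than the subject's, so entry at 0.25% and the absolute F-VASI change depend on who measures; the primary image endpoint does not

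*Combined protocol and SAP*

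**What the plan says.** Section 8.1.2 obtains the facial percentage by a palmar method that "uses the palmar surface area of the investigator's hand as an estimation guide and defines the surface of the hand including fingers" as 1.0% of total body surface area. Section 8.1.4 repeats this for the total body score: it "defines the surface of the evaluator's hand including fingers to be 1.0% of the total body surface area". Both sections name the assessor's hand. Neither these nor any other section uses the subject's hand, records hand size or calibrates assessors.

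Three measures rest on this unit:

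- **Entry.** Inclusion criterion 3 (Section 5.3) sets a minimum facial involvement, and Section 8.1.2 says that at screening and baseline the facial TBSA "will be calculated and must be at least 0.25" per cent.
- **F-VASI.** Section 8.1.2 gives "Facial VASI = % BSA x residual depigmentation". In Section 11.2 the first-listed secondary parameter "will be calculated as the mean change in Facial assessment of the Vitiligo Area Scoring Index (F-VASI) from Visit 2" to Week 24 and, where applicable, Week 48. No percent change is planned.
- **Total body VASI.** Section 11.2 keeps this as descriptive only.

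Sections 6.2 and 8 ask that one person assess a given subject throughout. Only where that cannot be kept up does Section 8 say that "an appropriate designee with overlapping experience with the subject and the study should perform the assessments". The primary parameter is an image-analysis ratio of detected area to the area of interest (Sections 8.1.1 and 11.2) and uses no hand.

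**The concern.** The text does not say whose total body surface is meant, but only the subject's makes sense for an entry criterion and a severity score. An assessor's hand is not calibrated to the subject's body. A large-handed assessor will under-read a small subject, and a small-handed assessor will over-read a large one.

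Three things follow:

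- The entry threshold is a quarter of a hand, so a modest difference in hand size can decide a borderline case.
- F-VASI is linear in the area, so its absolute change carries the same scale factor. With about 5 sites, the mean change averages values measured in different units.
- If the assessor changes, the score moves although the skin has not. Section 8.1.2 tells the investigator not to look at other visits' assessments when scoring, so such a shift would not be noticed at the visit.

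**Working it through.** The plan gives no figure to reproduce. Section 11.1 states 33 subjects and no formal power calculation. The check is therefore one of scaling.

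**Inputs from the documents:** one assessor hand = 1.0% (8.1.2, 8.1.4); entry threshold 0.25% (5.3, 8.1.2); F-VASI = %BSA × residual depigmentation (8.1.2); analysis as mean change (11.2).

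**Input not in the documents:** r = assessor hand area / subject hand area, assumed to lie between 0.80 and 1.25, with the subject's own hand taken as the 1% reference.

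**Formulas**
- Measured %BSA = true %BSA / r.
- Residual depigmentation is graded without the hand, so measured F-VASI = true F-VASI / r, and its absolute change also scales by 1/r.
- True involvement at a reading of 0.25% = 0.25 × r.
- Assessor changes from r1 to r2 with unchanged skin: the score is multiplied by r1/r2.

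**Entry and absolute change, one assessor throughout** (illustrative true F-VASI 1.00 falling to 0.50)

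| r | true 0.25% reads | true % needed to read 0.25% | true change -0.50 reads | percent change |
|---|---|---|---|---|
| 0.80 | 0.31 | 0.20 | -0.625 | -50% |
| 0.90 | 0.28 | 0.225 | -0.556 | -50% |
| 1.00 | 0.25 | 0.25 | -0.50 | -50% |
| 1.10 | 0.23 | 0.275 | -0.455 | -50% |
| 1.25 | 0.20 | 0.31 | -0.40 | -50% |

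The percent change does not depend on r: (0.50/r - 1.00/r) / (1.00/r) = -50% for any r.

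**Change of assessor, unchanged skin**
- Neighbouring values of r in the table: falls of 9% (1.00/1.10 - 1) to 12% (1.10/1.25 - 1), and rises of 10% (1.10/1.00 - 1) to 14% (1.25/1.10 - 1).
- Extremes of the assumed range: 0.80/1.25 - 1 = -36%, and 1.25/0.80 - 1 = +56%.

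**With the subject's hand as the unit,** r = 1 for every assessor. A reading of 0.25% then means 0.25%, the change of -0.50 reads -0.50, and a change of assessor adds no shift from hand size.

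**The case against.** The strongest reply is the same-assessor rule. Where it is followed, a fixed ruler cannot create a change from nothing: no change stays no change, the sign is kept and percent change is exact. Replacement is a fallback, not routine. This stands, and it limits the within-subject shift to subjects whose assessor actually changed. It does not touch the entry threshold or the size of the absolute change.

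The reach is also limited. The primary endpoint is unaffected, F-VASI is secondary, total VASI is descriptive, and this is a single-arm pilot without a hypothesis test. That stands, and it governs the weight of the point.

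The instrument is coarse in any case. The hand is called only a guide, and one step on the depigmentation grade from 25% to 50% doubles the score, which exceeds a ruler error of 10% to 25%. This too is fair. But a fixed, known scale error that can be removed at almost no cost should not be left on top of grading noise.

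The score is described as a modification of a validated scale. Whether the assessor's hand follows the source publication cannot be checked from the documents.

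A reader might go further and infer that F-VASI could routinely show an improvement of a third or more with unchanged skin. Take people of 190 cm/95 kg and 155 cm/50 kg. The Mosteller formula gives √(190×95/3600) = 2.24 m² and √(155×50/3600) = 1.47 m², a ratio near 1.53. Moving from the smaller to the larger as assessor would then lower the score by about 34%. The documents do not support this as a typical case. It needs extreme body sizes, hand area proportional to body surface, and a failure of the same-assessor rule for that subject.

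**Conclusion.** The point holds as a moderate one. As written, Sections 8.1.2 and 8.1.4 make eligibility at 0.25% and the absolute F-VASI change depend on the assessor's hand, and nothing in the plan corrects for it.

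That the dependence exists, and its direction, follow from the text. Its size rests on the assumed r. Between 0.80 and 1.25, the effective entry threshold is 0.20% to 0.31%, and an absolute F-VASI change is misread by -20% to +25%. A further shift arises only when the assessor changes: roughly 10% between similar assessors, and -36% or +56% at the assumed extremes.

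It would be wrong to conclude that the primary result is compromised, or that false F-VASI improvement is expected when one assessor follows a subject throughout.

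**What to change.** **Subjects not yet at baseline.** In Sections 8.1.2 and 8.1.4, define the subject's own hand, fingers included, as 1.0% of the subject's TBSA. Trace it once, keep the tracing in the source file, and have every assessor use it for entry, F-VASI and total VASI.

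**Subjects already past baseline.** Version 4.0 covers such subjects: footnote 14 to the Schedule of Assessments provides for some who finished Visit 10 before Amendment 3. Moving them to the subject's hand mid-series would create the very ruler switch described above. Either keep the baseline assessor's hand as the ruler throughout, or trace both the subject's and the assessor's hands and multiply every score in the series by r, using the r of whoever assessed each visit. Their entry decisions cannot be remade, so report which ruler was used.

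**All subjects.** Record assessor identity at each visit. In Section 11.2, add percent change from baseline in F-VASI beside the absolute change, and a sensitivity analysis excluding subjects whose assessor changed.

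**Cost.** A sentence in each of two sections, one paper tracing per subject (two where a series is converted) and slightly more analysis. No visits or staff are added. The subject's hand at 1.0% remains an approximation, so some calibration error will stay, but it will no longer depend on the size of the assessor's hand.
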